## ***E4. Statistical Methods***

Categorical variables will be described using frequencies and percentages. The Shapiro-Wilks test will be used to assess the normality distribution of continuous variables.

Normally distributed variables will be described by mean and standard deviation. Non-normally distributed variables will be described by median and interquartile range. Paired *t*-tests will be used to assess most differences between baseline and follow up. Wilcoxon signed rank tests will be used for the Diabetes Distress Scale scores and sub-scores.

Time in range data from the first 5 ( $\pm 1$ ) days of CGM wear will be compared to the second 5 ( $\pm 1$ ) days for any patients with at least 8+ days of CGM wear. Additional comparisons will be made with the follow-up CGM data recorded at the 3 or 6-month follow-up. Three month follow up data will be used when available. If the 3-month visit is missing, but there is a later 6-month follow-up, the 6-month visit data will be used. Two sample *t*-tests, and Wilcoxon rank sum tests (for the Diabetes Distress Scale), will be used to assess differences between groups in survey responses. The values  $p < 0.05$  are considered statistically significant. Statistical analysis generated using SAS version 9.4

Copyright © 2020 SAS Institute Inc., Cary, NC.

## ***E5. Missing Outcome Data***

Dataset will be assessed for missing-ness and noted in results. Statistical tests will be performed to compare groups with and without missing data, to assess for data missing at random.

---

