## **2.h Data Collection and Follow-up for Withdrawn Subjects**

Data collected from subjects will remain in the dataset, but no follow-up will be conducted on withdrawn subjects.

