### **D2 Schedule of Procedures**

**Eligibility and Consent:** If the patient is eligible and interested in the study, the research coordinator will meet with the patient and caregiver in an exam room for privacy and confidentiality. The research coordinator will explain the study and study procedures, read the informed consent form with the participant and caregiver, and allow time for questions on the study and consent form.

If the participant is less than 18 years of age, the parent will sign the consent form and the participant will sign the assent. If the participant is 18 years of age or over, the participant will sign the consent.

At the time of consent, 3 phone numbers are collected from the participant for future follow-up.

At the baseline visit, barriers to prior CGM use or sustained use will be recorded.

The certified diabetes educator (CDCES) will place the CGM and provide standardized education, including education on use of the Dexcom apps, including Dexcom G6 Dexcom Clarity, and Dexcom Follow (optional) for caregivers. The participant's Dexcom Clarity account will be connected to the clinic portal for remote viewing of data.

The nurse/CDCES will follow up with the patient by phone in 5 days (4-6 days if day 5 falls over a weekend) and again at 10 (9-11) days at the end of the CGM session. Assessment and education during these follow-up phone calls will include report of behavior changes related to blood glucose monitoring and insulin administration, and nurse/CDCES recommended dose adjustments based on observed patterns, as well as education on obtaining personal CGM. CGM data (when available) will be recorded.

---

At the participant's next follow-up visit at 3 months (or up until 6 months if a visit is cancelled), use of personal CGM will be recorded, in addition to Hemoglobin A1c measured at that visit, questions about behavioral changes, and CGM data, if available.

Questionnaires will be administered before and after initiation of the CGM and at their routine diabetes clinic visit 3-months later to assess changes in psychosocial outcomes of diabetes distress and hypoglycemia worry. Surveys will be administered via REDcap survey.

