### **E. Statistical Plan**

#### ***E1. Sample Size Determination and Power***

We calculated the sample size to detect a 10% difference in TIR from the first 5-days compared to the second 5 days of CGM wear. Assuming a TIR SD of 18% (20), a 2-sided alpha level of 0.05 and 80% power, a sample size of 28 participants was required. Allowing for 30% attrition, we planned to recruit 40 participants.

---

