## ***E3. Analysis Plan***

Primary outcome variable.

The primary outcomes of the study were change in TIR from the first 5 days compared to the second 5 days of CGM wear, and change in HbA1c level from baseline to follow up at 3-6 months, both assessed with paired *t*-tests.

Secondary outcome variables.

Secondary endpoints included behavioral modification assessed via questions during 5-day and 10-day follow up call. Change in patient-reported outcomes through surveys assessing quality of life and diabetes-distress compared between baseline and follow-up after trial CGM use.

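### Section E5's comparison of participants with and without data cannot assess missing at random, no step follows its result, and no sensitivity analysis is planned for either primary outcome

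*Combined protocol and SAP*

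**What the plan says.** Section E5 has two sentences. The first commits to reporting: "Dataset will be assessed for missing-ness and noted in results". The second gives the test and its purpose: "Statistical tests will be performed to compare groups with and without missing data, to assess for data missing at random". It names no variables to compare and no action for a significant or a non-significant result. Sections E1 to E5 contain no imputation, model-based analysis or sensitivity analysis.

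Section E3 sets two primary outcomes. One is the change in TIR between the two halves of sensor wear. The other is "change in HbA1c level from baseline to follow up at 3-6 months, both assessed with paired" t-tests. A paired test uses only participants with both values. Section E4 limits the TIR comparison further, to be made "for any patients with at least 8+ days of CGM wear".

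The plan provides for some loss. Section E1 says: "Allowing for 30% attrition, we planned to recruit 40 participants". Section D2 says "CGM data (when available) will be recorded", and section 2.h says "no follow-up will be conducted on withdrawn subjects". Some provisions limit loss: a replacement sensor (2.e), three phone numbers taken at consent (D2), and use of a 6-month visit when the 3-month visit is missing (E4).

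**The concern.** Missing at random means that, given what was observed, the chance of being missing does not depend on the unseen value. A comparison of observed characteristics carries no information on that last part. A significant difference is evidence against missing completely at random and is fully compatible with missing at random. A non-significant difference is compatible with every mechanism, including loss driven by the unseen change itself. So the test cannot do the job that E5 gives it.

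A reader could take a non-significant result as reassurance that the completers represent everyone enrolled, or a significant one as proof of bias. Neither follows. With no sensitivity analysis planned, a reader also cannot see how far each primary result depends on the people who were not analysed.

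**Working it through.** **Inputs.** From E1: difference 10 points, SD 18, two-sided alpha 0.05, 80% power, 28 evaluable, 30% attrition, 40 recruited.

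**1. The plan's own figure.** Paired t-test, noncentral t, noncentrality = (10/18)√n. Power is 79.4% at n = 27 and 80.9% at n = 28, so 28 reproduces if 18 is the SD of the paired difference. Then 28/(1 − 0.30) = 40. The sample size is not in error. The inflation protects precision; it does nothing about bias.

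**2. Power of the E5 comparison at 28 versus 12.** Two-sample t-test, df 38, critical value 2.02, noncentrality = d/√(1/28 + 1/12) = d/0.345.
- d = 0.5 SD: noncentrality 1.45, power 29%.
- d = 1.0 SD: noncentrality 2.90, power 81%.

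At this size, a non-significant result says little even about missing completely at random.

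**3. Whether the check tracks bias.** This is a simulation under assumptions, not a statement about this trial. Assumed: 40 enrolled, 30% loss, true change 0, SD 18 in each window, correlation 0.5 (change SD then 18), and a check on first-window TIR known for everyone. The two figures in each cell are for retention log-odds of 0.5 and 1 per SD.

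| Retention depends on | Bias of paired mean (points) | Check significant |
|---|---|---|
| own change | +2.6 / +4.6 | 10% / 22% |
| average TIR | 0 / 0 | 22% / 57% |
| first-window TIR | −1.3 / −2.3 | 27% / 72% |

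Reversing the sign of the dependence reverses the sign of the bias. The check flags harmless loss (row 2) more often than the most harmful loss (row 1), but it does pick up row 3. At 20% loss the row 1 bias falls to +1.8 / +3.1, and at 10% to +0.9 / +1.6.

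**4. What a sensitivity analysis would show for TIR.** Assumed: completers at the planned +10, change SD 18, missing participants averaging no improvement (delta = −10), completer standard error kept. With n completers, estimate = 10 × n/40, SE = 18/√n, df = n − 1.

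| Loss | n | Estimate | SE | t | p | Completers-only p |
|---|---|---|---|---|---|---|
| 10% | 36 | +9.0 | 3.00 | 3.00 | 0.005 | 0.002 |
| 20% | 32 | +8.0 | 3.18 | 2.51 | 0.017 | 0.004 |
| 30% | 28 | +7.0 | 3.40 | 2.06 | 0.049 | 0.007 |

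The shift at which p reaches 0.05 is (t-critical × SE − 10)/(loss fraction).
- 10% loss: (6.09 − 10)/0.1 = −39.1, a missing-group mean of −29.1.
- 20% loss: (6.49 − 10)/0.2 = −17.6, a mean of −7.6.
- 30% loss: (6.98 − 10)/0.3 = −10.1, a mean of −0.1.

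**5. Dependence on the variance method at 30% loss, estimate +7.0.**
- SE 18/√40 = 2.85: p = 0.018 to 0.021 (df 39 or 27).
- Fixed delta, SE 3.40: p = 0.049.
- Delta-adjusted multiple imputation, SE 3.55: p = 0.059.
- Twelve zeros filled in as if observed, SE 2.48: p = 0.007, no more cautious than completers only.

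The method therefore has to be named in advance.

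**6. HbA1c.** The documents give no SD of change and no loss rate for this outcome, so no corresponding figure is offered.

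**The case against.** The strongest reply is that E5 does what small pilots ordinarily do: it reports missingness and compares those with and without data, so readers get real information. On this view only the phrase naming missing at random is wrong. That is largely fair, and the comparison is worth keeping; step 3 shows it can detect loss that depends on first-window TIR. But loose wording still needs correcting, and it does not explain why nothing follows the result.

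Second, 30% is an inflation allowance, not a forecast, and the replacement sensor, phone numbers and 6-month substitute should reduce loss. This stands, and it is why step 4 shows a range.

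Third, short wearers may be outside the TIR target, since E4 restricts that comparison to at least 8 days of wear. Assigning them a second-window change answers a wider question. This stands too: the primary TIR result should be described as applying to that group, with the all-enrolled analysis as sensitivity only.

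Fourth, if the missing mean is taken as exactly zero and known, the SE shrinks to 0.7 × 3.40 = 2.38 and p stays at 0.007. That is arithmetically right, but it treats an unknown quantity as known.

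A reader might infer from the concern that the primary results will be biased in favour of CGM. The documents do not support this. Nothing in them shows that loss is related to change, and the bias could be in either direction or absent.

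**Conclusion.** The purpose that E5 gives its test is wrong as written, and a cheap sensitivity analysis is missing for both primary outcomes. The first part rests on the definition of missing at random and needs no assumption about this trial.

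The size of the consequence is modest. For TIR, under the assumptions of step 4, significance survives the no-improvement case comfortably at 10% and 20% loss and only barely at 30%. A general claim that the TIR result is fragile would therefore go too far. For HbA1c the size is unknown. The flag rates in step 3 depend on assumed mechanisms and on a chosen check variable; E5 names none, so they illustrate the principle and predict nothing here. Severity is minor to moderate for an uncontrolled pilot.

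**What to change.** Keep the paired t-tests as primary and keep E5's first sentence. Replace the second with:

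> Participants with and without each primary outcome will be compared on baseline characteristics; this can give evidence against missing completely at random but does not establish missing at random. For each primary outcome, a delta (tipping-point) sensitivity analysis over all enrolled participants will be reported. The mean change in participants with missing outcomes will be shifted from the completer mean in steps to no improvement and beyond, with the completer standard error kept (fixed delta), and the shift at which p reaches 0.05 will be reported. Zeros will not be filled in as if observed. If the result is lost at or before the no-improvement case, the conclusion will be limited to participants with complete data. For TIR, the primary result will be described as applying to participants with at least 8 days of wear.

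The cost is SAP wording and modest programming, with no new data, visits or participants. The downside is possibly a more cautious conclusion. Sections A1, E1 and E3 are partly in the past tense; if the analysis has already been done, the sensitivity analysis should be reported as post hoc.

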## ***F. Data Handling and Record Keeping***

---

## ***F1. Confidentiality and Security***

All data for this study will be recorded, stored and analyzed in a password-protected file on a HIPAA-compliant and secure drive through Johns Hopkins Medicine, called the SAFE (Secure Analytic Framework Environment) Desktop. This secure environment is provided by JHM and includes productivity software and statistical software. Storing the Data on the SAFE Desktop complies with federal and institutional requirements to protect patient data. Using SAFE reduces the risk of copying data to an unencrypted desktop or device because the SAFE provides the tools to securely analyze and share PHI/PII all within the SAFE environment. Only authorized persons will have access to SAFE Desktop, login and passwords will not be shared and databases will not be left unattended to further minimize risk of loss of confidentiality.

## ***F2. Records Retention***

Informed consent documents will be securely stored in a locked file cabinet within a locked office. Informed consents will also be scanned into the participant's electronic medical record. Data will be stored for up to 7 years.

### ***G2. Funding Source***

Funding for this study is provided by the Johns Hopkins Children's Center Innovation Award (PI: [name]) and an investigator initiated research grant from Dexcom, Inc (PI: [name])

### ***G3. Subject Stipends or Payments***

Participants will receive a \$10.00 gift card, and a parking pass at the baseline study visit and a \$10.00 gift card at the completed follow-up visit.

